However, the effective modulation of brain activity may depend not on the absolute current density, but on the current flow that is normal to the cortical surface. This is because the neurons of the cortex are aligned perpendicular to the cortical surface, and the induced current serves to alter neuronal polarization along the apical dendrite to somatic axis of the cortical pyramidal neurons (Datta, Zhou, Su, Parra, & Bikson, 2013). Wagner et al (2004) point out that as little as 30% of the current induced by TMS may be oriented normal to the cortical surface. This implies that TEN, which can be directed from the 256 channel array to be oriented mostly normal to the cortical surface, may achieve effective dosage that is within a factor of 10 less than the magnitude of the effective TMS induced current.

Importantly, a major advantage of TEN over TMS is the ability to reach deep sources. In the simulations of TMS by Wagner, et al. (2004), the depth penetration of TMS was 2 cm into brain tissue, where it reached only the crown of the gyrus, and there the current was largely tangential to the gyral crown (rather than surface normal). We must assume, therefore, that the targeting in the existing studies of slow rTMS for epilepsy (Fregni, et al., 2006; Sun, et al., 2012) was highly approximate. Although Fregni et al. used focal cortical dysplasias to guide targeting, it is highly unlikely that these were all within 2 cm of the cortex, or that effective targeting of current direction was achieved.

Therefore, considering these several factors, we can reasonably expect that the electrical dosage of the GTEN 100, with the safety and comfort level set at $200 \mu\text{A}$ per electrode for the study protocol pulses (**Figure 10**), when targeted appropriately to the epileptogenic focus with the 256 array and the high resolution head model, will be an effective treatment for seizure suppression.

Clinical Feasibility Trial Design

The goal of this unblinded and uncontrolled (“open-label”) feasibility study is to evaluate the safety, comfort, and preliminary efficacy of GTEN 100 treatment in achieving temporary suppression of epileptic activity, as assessed primarily by spikes and secondarily by seizures. The GTEN 100 applies small, electrical currents (up to $200 \mu\text{A}$ per electrode and up to 2 mA total) in a pattern that targets the cortical site of epileptiform discharges in order to decrease the excitability of the epileptogenic cortical tissue.

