- (3) A history or condition of status epilepticus or psychogenic seizures.

- (4) Presence of a cardiac pacemaker, vagus nerve stimulator, or metal implantation in the body (other than the teeth) including neurostimulators, cochlear implants, and implanted medication pumps.
- (5) Previous surgery involving opening the skull.
- (6) Allergy to or condition contraindicating lidocaine.
- (7) Unable to express presence of pain or discomfort.

Escape Criteria

For individual patients, the study will be terminated for any of the following reasons:

- (1) Unacceptable discomfort or pain at stimulation currents of 200 μ A.
- (2) A tonic-clonic seizure occurring during a stimulation session.
- (3) Emergence of a first-in-life tonic-clonic seizure at any time during the study.
- (4) Status epilepticus.
- (5) A two-fold increase of seizure frequency over the baseline seizure frequency. If the frequency of seizures is very low, then an apparent increase during treatment (not reliably quantified as a two-fold increase) will be discussed with the patient, family, physician and Study committee.

The entire study will terminate if 5 subjects meet escape criteria.

Baseline Evaluation

During a one-month pre-treatment baseline evaluation period, the patient (and/or family) will maintain the seizure diary, which will be reviewed by the study coordinator in a phone contact once per week. In addition, two two-hour routine dEEG evaluations will be conducted in the baseline evaluation period, including the opportunity for sleep for patients who may have interictal events in sleep or drowsiness. Each baseline evaluation also includes the California Verbal Learning Test, and the Quality of Life in Epilepsy report.

Probe Treatment and Evaluation

The GTEN Plan is developed to apply current pulses to the epileptic focus, as it is identified from the dEEG source localization of the spike onset. The GTEN Plan will often include more than one treatment option, primarily depending on the orientation of the cortical region identified as the epileptic focus. To evaluate a treatment targeting option, a probe treatment may be conducted, consisting of one 17-min pulsed treatment block (Figure 10) followed by one hour of dEEG evaluation and spike counting. If multiple targeting options are evaluated, the one with the best evidence of spike suppression will be selected for the 5 session treatment intervention.

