The primary endpoint is a temporary suppression of epileptic spikes. With assessments of spike rates at weeks 2, 4, 8, 16, and 24, the study will allow estimation of how temporary a suppression is achieved by the one-week treatment. The routine dEEG sessions typically collect dEEG for over an hour, and spike rates per hour will be the standard metric. To be successful, and to warrant progression to a randomized clinical trial, this clinical feasibility study must demonstrate successful targeting and suppression of the epileptogenic zone, as evidenced by temporary but statistically significant spike suppression in contrast to the pre-treatment baseline. All spike rates (baseline, treatment, and follow-up) will be counted as spikes per hour and classified in relation to waking or sleep stage (N1, N2, N3).

Secondary Endpoints and Study Success

The secondary endpoint is monthly suppression of seizures, assessed by the seizure diary each month for six months following treatment, in comparison to the mean seizure frequency for the one-month pre-treatment evaluation baseline. It is clearly advantageous if there is seizure as well as spike suppression as we plan the design of the pivotal trial.

Additional secondary endpoints will be (1) any improvement of cognitive function testing beyond the practice effect (estimated from norms and the improvement in the sham control group); (2) any improvement in quality of life ratings.

Study Monitoring Committee

The safety and comfort decisions for each patient are made by the epileptologist at each site. The safety, comfort, and efficacy of each treatment protocol across sites are reviewed by the Study Monitoring Committee. Vigilance will be maintained throughout the pivotal study to insure safety (no provoked seizures and no adverse effect to non target brain regions). Treatment will be discontinued for any patient that shows treatment-induced seizures, defined as seizures that are not the patient's typical seizures or that occur twice as frequently as the patient's typical seizures, as assessed during baseline. If there are more than five patients with worsening seizures (meeting escape criteria as stated above), the treatment will be suspended at that site. The Study Monitoring Committee (and the FDA when possible) will decide if the trial with that treatment should be terminated at all sites.

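### Two study-level safety stopping rules contradict each other: five escapes end the whole study, yet more than five worsened patients suspend only one site

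*Protocol*

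**What the plan says.** Clinical Feasibility Trial Design, Escape Criteria, lists five reasons for ending an individual patient's participation. The first is "Unacceptable discomfort or pain at stimulation currents of 200" μA. The others are a tonic-clonic seizure during a stimulation session, a first-in-life tonic-clonic seizure, status epilepticus, and a doubling of seizure frequency over baseline. The list is followed by a rule for the whole trial: "The entire study will terminate if 5 subjects meet escape criteria". That sentence has no site qualifier and leaves no discretion.

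Study Monitoring Committee, later in the same part of the protocol, gives a second rule: "If there are more than five patients with worsening seizures (meeting escape criteria as stated above), the treatment will be suspended at that site". It adds that the committee, and the FDA when possible, "will decide if the trial with that treatment should be terminated at all sites".

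Both sentences are current body text. No sentence says which one takes precedence.

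**The concern.** These are the protocol's only numerical safety limits at study level, for a device that the protocol itself acknowledges may worsen seizures in patients with epilepsy. They differ in four respects: the count (five, or more than five), the event (any escape criterion, or worsening seizures only), the scope (the entire study, or one site) and who decides (an automatic rule, or a committee).

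Two safety rules can coexist if they form tiers, with a lower count for a milder local action and a higher count for a study-wide stop. Here the order is reversed. A coordinator who works from the Escape Criteria would stop at the fifth escape. One who works from the Study Monitoring Committee paragraph could go on treating, believing that the protocol allowed it. What is at stake is whether sites and committee apply the same limit.

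**Working it through.** No figure in the protocol has to be reproduced. The check is whether both rules can be in force together.

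**Inputs**

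| | Rule A (Escape Criteria) | Rule B (Study Monitoring Committee) |
|---|---|---|
| Event counted | any of the five escape criteria, pain included | worsening seizures that meet those escape criteria |
| Trigger | 5 subjects | more than five, so 6 patients |
| Action | entire study terminates | treatment suspended at that site |
| Termination at all sites | automatic | committee decision, with the FDA when possible |

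The trial design section plans three sites. The section on changes to the Harborview consent form says that one is active.

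**Can Rule B be reached while Rule A is obeyed?** Let w be the number of patients with worsening seizures who meet escape criteria, and o the number who meet only some other escape criterion.

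- Rule A triggers when w + o ≥ 5.
- Rule B triggers when w ≥ 6.
- If w ≥ 6, then w + o ≥ 6, which exceeds 5. Rule A was therefore met earlier.

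Enumerating w and o from 0 to 11 gives no state with w > 5 and w + o < 5. Rule B does not say whether its count is per site or pooled, but the result is the same: six worsened patients at one site are also six in the study.

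**What each rule requires, taking worsening seizures only, at the one active site**

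- w = 4: neither rule is triggered.
- w = 5: Rule A terminates the study. Rule B requires nothing.
- w = 6: Rule A does not allow this state to arise. Rule B suspends the site and passes the question of the other sites to the committee.

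**Size of the gap.** Assume that criterion 1 is pain and that the other four criteria count as worsening seizures. If k of the first five escapes are for pain, then w = 5 − k, and Rule B is short of its trigger by 6 − (5 − k) = k + 1 patients.

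- k = 0: 1 patient
- k = 1: 2 patients
- k = 2: 3 patients

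The protocol gives no rate of pain escapes, so the values for k > 0 only show the direction. It also states no sample size and no worsening rate, so no probability of stopping, and no number of patients treated beyond the limit, can be derived.

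**The case against.** The strongest reply is that Rule A is unconditional. A site that obeys every sentence stops at five and breaches nothing in Rule B, which is then merely redundant. With one active site, suspension there would in any case halt all current treatment, so for worsening seizures the practical difference is one patient. Each patient is also covered separately by the individual escape criteria, by discontinuation for treatment-induced seizures (Study Monitoring Committee) and by suspension on a two-fold increase (Monitoring of Risk).

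All of this stands, and it limits the point. It does not remove it: Rule B describes a trial that may still be running elsewhere after more than five worsened patients, and Rule A excludes such a trial.

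A reader might infer more than the text supports in four ways.

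- *That the two rules prescribe opposite actions at the fifth escape.* They do not. Rule B is silent until a sixth worsened patient, and an untriggered rule does not order treatment to continue.
- *That automatic termination at five is left open.* Rule A says plainly that the study ends.
- *That the gap is several patients wide across three sites.* This needs all three sites open and a per-site count. Only one site is active, and the count is unspecified.
- *That the committee paragraph is leftover text and can be ignored.* There are signs of uncorrected wording. The paragraph says "Vigilance will be maintained throughout the pivotal study to insure safety" and "efficacy of each treatment protocol across sites are reviewed by the Study Monitoring Committee", and the section before it has practice effects "estimated from norms and the improvement in the sham control group", although the trial design section opens with "The goal of this unblinded and uncontrolled". The Overview says that only the pulsed protocol remains, so the treatment in question is now the whole trial. These signs may explain how the conflict arose, but they do not say which rule governs.

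**Conclusion.** Wrong as written: an internal inconsistency in a safety stopping threshold. If the Escape Criteria rule is followed, the Study Monitoring Committee rule can never operate. If the committee rule is followed instead, treatment continues past the point at which the protocol says the entire study ends.

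At the one active site the difference is one patient for worsening seizures. It widens by one for each pain escape among the first five. The subset argument rests only on the committee sentence's own reference back to the escape criteria. The size rests on reading criteria 2 to 5 as worsening seizures, which the protocol does not spell out.

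This is not a gap in the protection of individual patients, and the stricter rule is already in the text. It should be corrected because a numerical stopping limit has to read the same way to every site and to the committee.

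**What to change.** Keep the Escape Criteria sentence as the single study-level stopping rule, and state in it that the five subjects are pooled over sites and that any listed escape criterion counts, pain included. In Study Monitoring Committee, delete both the more-than-five site-suspension sentence and the sentence that leaves termination at all sites to the committee, or align both to the five-subject rule. If the sponsor wants to keep a site-level suspension as an earlier tier, its count must be below five, and it must say whether it is counted per site.

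The cost is one amended paragraph, with no extra patients, visits or procedures.

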For this safety and feasibility study, two clinical sites are being planned in the US (Eugene, Seattle) and one in China (Shanghai). An expert epileptologist will provide medical guidance at each site. The Chair of the Study Monitoring Committee will not be associated with these sites or with EGI: [name], Cincinnati Children's Hospital Medical Center. Racial and gender composition will be as it appears in each sample. Study protocols and safety procedures have been approved by IRBs in Eugene and Seattle, and are under review at Huashan Hospital in Shanghai.

Patient Recruitment

Adult and adolescent patients (12 and older, including males and females) are recruited who continue to have seizures after having achieved adequate dosage on each of two antiepileptic drugs. Patients are selected who have focal spikes (and other discharges of focal onset, including seizures) identified through Electrical Source Imaging (ESI) applied to a routine dense array EEG (dEEG) evaluation. All patients agree to maintain their current antiepileptic drug dose throughout the study, including the two month baseline and the two month follow-up period.

Inclusion Criteria

- (1) Partial onset seizures (simple or complex) with failure of adequate seizure control after prior use of at least 2 anti-seizure drugs at effective doses.
- (2) A clearly identified and localizable focus of epileptiform discharges, as defined by the discharges (typically epileptiform spikes) and as identified by dEEG assessment through one or more routine clinical dEEG evaluations.
- (3) Two or more partial seizures, with or without secondary generalization, in the last month, but less than 10 seizures per day.
- (4) Anti-seizure drug regimen has remained unchanged for the month before study entry, and there is reasonable likelihood of stability for the duration of the study, with the exception of allowing short-term rescue medications, such as lorazepam.
- (5) A history of epilepsy for at least 2 years. 33

Exclusionary Criteria

- (1) If of childbearing potential, the patient must agree to use an effective method of birth control during the study and cease participation if pregnant.
- (2) A history or condition of progressive brain disorders, serious systemic diseases, symptomatic cerebrovascular disease, cardiac disease, or alcohol abuse. Special conditions, for example, non-malignant brain tumors and vascular malformations, can be considered for entry on a case-by-case basis.

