- There is minimal risk of the treatment. The slow pulsed electrical neuromodulation has been applied in several studies of epilepsy with the TMS procedure, and there is no evidence that it causes seizures. Transcranial electrical stimulation (tDCS) has been applied in several experimental studies of patients with epilepsy, with no evidence that it causes seizures. Nonetheless, there is always a small risk of causing seizures, and medical procedures are in place both to monitor for seizures (with the EEG recording in each session) and to provide first aid if a seizure occurs.

- The primary feeling of the electrical current is a tingling sensation, and there is risk of minor itching and/or scalp pain. A small amount of lidocaine is mixed in the electrolyte to minimize the pain at the electrode site, and the procedures will be adjusted to assure that any discomfort is acceptable to the patient. Each patient should understand that they should speak up if there is any discomfort, that the technician is trained to carefully monitor their comfort level, and that they can quit the treatment at any time by simply saying they want to quit. If there is any emergency, the patient is shown how to simply pull the Geodesic Sensor Net off the head.

Changes to the Harborview Informed Consent Form

The Informed Consent Document (ICD) approved with the GTEN IDE was the EGI Consent Form (GTEN) 12/29/2014. This was rewritten to conform to the format of the University of Washington IRB and approved by the UW IRB. It was then modified to include the probe test (as described in the present protocol) and approved in November 2015. A minor error (stating the probe test was 10 min rather than 17 min) was corrected and the correction was approved March 9, 2016.

The EGI Parental Consent Form approved with the IDE is unchanged, but is not in use because the only active trial site (UW Harborview) is not enrolling adolescents.

Both the EGI IRB Consent form of December 29, 2014 (approved with the IDE) and the UW IRB Consent Form (proposed for this trial with the present Supplement) are attached.

With the exception of the probe test, there are only minor differences in these consent forms, involving the change of format to the UW IRB Consent Form format. Following is a section-by-section summary of the revision, emphasizing where the same information from the (IDE approved) EGI IRB Consent Form is included in the UW IRB Consent Form.

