The dEEG is reviewed after each treatment and follow up session, by visual inspection by a trained electroencephalographer and with an automated spike detection and clustering algorithm (EGI's Spike Beacon software), with the quantitation reported as a trial endpoint. If there is an apparent change in the spike (and possibly seizure) localization, as indicated by the spike topography clustering, Electrical Source Imaging is conducted with GeoSource to determine if there is a change in localization. If there is a change in localization, or if there is an increase in spike frequency of over one standard deviation compared to the baseline sessions, or if there is non typical seizure activity, the results are conveyed to the epileptologist supervising the clinical trial to evaluate the risk for the patient's continuation of the trial.

The experimental procedures for each patient session are summarized in Table 2.

Monitoring of Risk

A daily diary with a count and description of seizures is reviewed at each session (treatment and follow up). If there is an increase in seizures of two-fold over the patient's baseline levels, the patient's treatment is suspended and the safety of the treatment is evaluated by the epileptologist, patient, and family. In the follow up sessions, routine dEEG evaluations, cognitive function assessments, and quality of life ratings are conducted once each week for three weeks following the treatment, and then week 8. At each follow up session, cognitive function is assessed with the California Verbal Learning Test, a widely used and easily administered test (www.pearsonclinical.com), and quality of life is assessed with the Quality of Life In Epilepsy Questionnaire (http://www.rand.org/health/surveys_tools/qolie.html).

Overview of Study Protocol

Table 2 presents an overview of the treatment protocol. An exception is that for the first ten patients the dEEG will be monitored for seizures for 3 hours after the first treatment session.

Session	Procedure
Pre-Treatment Evaluation	Review of seizure diary each week for one month. Two routine dEEG evaluations to capture epileptiform discharges (ED), including spikes and seizures. MRI when available to determine possible malformations of cortical development and build individual head model.

Session	Procedure

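### The study-level stopping rule is given twice, and the two versions cannot both be followed at the fifth escape

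*Protocol*

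**What the plan says.** The closing line of Escape Criteria reads: "The entire study will terminate if 5 subjects meet escape criteria". It follows a list of five reasons for ending an individual patient's participation: unacceptable pain, a tonic-clonic seizure during stimulation, a first-in-life tonic-clonic seizure, status epilepticus, and "A two-fold increase of seizure frequency over the baseline seizure frequency". It has no site qualifier and names nobody who decides.

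Study Monitoring Committee says: "If there are more than five patients with worsening seizures (meeting escape criteria as stated above), the treatment will be suspended at that site". It continues: "The Study Monitoring Committee (and the FDA when possible) will decide if the trial with that treatment should be terminated at all sites".

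On sites, Clinical Feasibility Trial Design plans three (two in the US, one in China). Changes to the Harborview Informed Consent Form states that "the only active trial site (UW Harborview) is not enrolling adolescents".

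The seizure-doubling criterion that feeds both counts appears twice more. Study Monitoring Committee discontinues treatment for seizures that "occur twice as frequently as the patient's typical seizures, as assessed during baseline". Monitoring of Risk says: "If there is an increase in seizures of two-fold over the patient's baseline levels, the patient's treatment is suspended", with an evaluation to follow.

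**The concern.** Both sentences are current text, and neither says which prevails. They disagree on the threshold, on which events count, on how far the consequence reaches, and on who makes the decision.

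The trial is open-label and uncontrolled, and the sponsor accepts the FDA's view that the device may carry a significant risk of worsening seizures in this population. A stopping rule has to be unambiguous when it is reached. Here, at the fifth escape, a site reading one section would regard the trial as over, while a committee member reading the other would see no reason to act. Each would be following the protocol.

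**Working it through.** The protocol derives no operating characteristic for either rule, so there is no figure to reproduce. The check is a comparison of the two rules.

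**Inputs**

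- Rule A (Escape Criteria): let *a* be the number of subjects in the whole study who have met any escape criterion. The study terminates when *a* ≥ 5.
- Rule B (Study Monitoring Committee): let *b* be the number of patients with worsening seizures who meet the escape criteria. More than five means *b* ≥ 6. The consequence is suspension at a site, then a committee decision about all sites.

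**Step 1: relation between the counts.** Every patient in *b* has met an escape criterion and so is also in *a*. Hence *b* ≤ *a* always, and *b* ≥ 6 implies *a* ≥ 6, which exceeds 5. Rule B cannot be reached without Rule A having been reached too.

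**Step 2: the rules case by case, at a single site**

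| Escapes so far | Rule A | Rule B |
|---|---|---|
| 4, all worsening seizures | no action | no action |
| 5, all worsening seizures | whole study terminates | no action |
| 6, all worsening seizures | study already terminated at the fifth | site suspended; committee decides on the rest |
| 5, all for pain | whole study terminates | no action (*b* = 0) |

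**Step 3: consequence of each choice.** Under Rule A, the trial is over before *b* can reach 6, so the site suspension and the committee's decision on all-site termination are dead text. Under Rule B, the fifth escape has no study-level effect, so the line in Escape Criteria is not honoured.

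**Step 4: can they be layered?** A layered scheme would suspend a site at a lower count and end the study at a higher one. Here the order is reversed: the narrower action needs 6 and the wider one needs 5.

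**Step 5: do they concern different treatments?** Rule B speaks of the trial with a particular treatment, which would make sense with two protocols under test. The Overview says that only the Pulsed GTEN protocol will be used, so stopping that treatment stops the trial.

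**The case against.** The best defence is that patients are protected well before either rule matters. Stimulation stops for discharges that suggest kindling, each patient has escape criteria, and the site epileptologist evaluates any doubling of seizures. The committee also reviews safety across sites throughout. All of this stands, so it would be wrong to say that a fifth escape has no consequence at all; it has none at study level under Rule B. None of it settles which study-level rule applies.

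A reader might infer four stronger points, which the document does not support.

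- **A much larger gap with three sites.** If Rule B is counted separately at each site, 3 × 5 = 15 patients could worsen before any suspension is required. The sentence attaches the site to the suspension, however, and does not say that the count is per site. That reading is an inference, and it also requires Rule A to be ignored.
- **No settled baseline for the doubling rule.** Baseline Evaluation, Secondary Endpoints and Table 2 all put the seizure-diary baseline at one month. The two-month wording in Patient Recruitment concerns keeping drug doses stable, and the three-month wording in Mitigating the Risk of Seizures in Normal Operation concerns dEEG evaluations. They look like leftovers and do not define the diary comparator.
- **Three conflicting consequences for the patient.** Suspending treatment, evaluating, and then discontinuing or ending participation can largely be read as a sequence, with the site epileptologist making each patient's safety decisions.
- **An unusable doubling rule because no counting window is given.** The window is unstated, but that is mainly an omission. The criterion refers to a frequency, the diary is reviewed weekly and at sessions, and very low rates have a discussion route. Any estimate of chance crossings would rest on seizure rates and dispersion that the document does not give.

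**Conclusion.** The contradiction is real and follows from the wording alone, with no statistical assumption. At the one active site the difference is 5 against 6 patients, any escape criterion against worsening seizures, and automatic against committee-decided termination. If the committee section's count is taken per site, the gap widens with three sites, but that depends on an inferred reading. No probability of stopping is attached to either rule, because the protocol states no sample size. The remaining irregularities around the doubling criterion are matters of tidying.

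**What to change.** State one rule in both Escape Criteria and Study Monitoring Committee. When 5 subjects across all sites have met any escape criterion, enrolment and treatment stop at once at every site. The Study Monitoring Committee, with the FDA when possible, then decides whether termination is permanent. Delete the separate trigger of more than five patients with site-only suspension.

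As minor tidying, say that the doubling rule compares seizure rates with the one-month diary baseline wherever it appears (Escape Criteria, Study Monitoring Committee, Monitoring of Risk). Align the two-month wording in Patient Recruitment and the three-month wording in Mitigating the Risk of Seizures in Normal Operation with the current schedule.

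The change needs no new data, only edited text and whatever regulatory and IRB handling a protocol amendment requires. The main cost is that final termination becomes a committee decision, whereas Escape Criteria now makes it automatic; the halt at 5 stays automatic. Because pain still counts, five withdrawals for discomfort would also halt the trial, and the committee could then decide whether it should resume.
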